5.3. Lifestyle Considerations

Not applicable.

5.4. Screen Failures

Screen failure is defined as participants who consent to participate in the clinical study but are not subsequently randomly assigned to study intervention. A minimal set of screen failure information is required to ensure transparent reporting of screen failure participants to meet the CONSORT publishing requirements and to respond to queries from regulatory authorities. Minimal information includes demography, screen failure details, eligibility criteria, and any SAE.

5.4.1. Allowed Retesting of Screening Investigations

Repeating laboratory tests during the screening period does not constitute rescreening.

In particular, the following laboratory tests may be repeated **1 time** during the screening period to determine a participant's eligibility for randomization:

- tests for SLE, such as ANA, anti-dsDNA, and/or anti-Sm antibodies
- tests related to lupus nephritis, and
- clinical chemistry, hematology, and calculation of eGFR.

See Section 8.2.6 for retesting related to TB.

5.4.2. Rescreening of Individuals Who Failed Screening

Informed consent for rescreenings

Individuals who are to be rescreened must first sign a new ICF (Appendix 10.1, Section 10.1.3). Such individuals will be assigned a new participant number.

Rescreening after failure to meet study entry criteria

An individual who does not meet the criteria for participation in this study may be rescreened **1 time** if the reason for the screen failure has resolved and if the sponsor has approved the rescreening. The interval between the failure to meet study entry criteria and the start of rescreening should be at least 4 weeks.

Rescreening for administrative reasons

An individual may be rescreened **1 time** for an administrative reason, including, for example, but not limited to, falling out of the screening window because of scheduling conflicts. The sponsor does not need to approve rescreening for an administrative reason. The rescreening can start immediately after the administrative reason has resolved.

Procedures not required to be repeated during rescreening

Individuals in rescreening who have already completed the protocol-required screening CXR or TB tests are not required to repeat these procedures if they were performed within 90 days before the date of signing the rescreening ICF. However, these procedures can be repeated at the discretion of the investigator.

6. Study Intervention

Study intervention is defined as any investigational intervention, marketed product, placebo, or medical device intended to be administered to/used by a study participant according to the study protocol.

6.1. Study Interventions Administered

Study interventions, and, if applicable, investigational medical devices are described in the ISAs. A placebo control group is included in the design of each ISA.

6.2. Preparation/Handling/Storage/Accountability

Study interventions will be stored, inventoried, reconciled, and destroyed according to applicable regulations.

Site responsibilities

The following are responsibilities of the investigator or his or her designee:

- The investigator or designee must confirm appropriate storage conditions have been maintained during transit for all study intervention received and any discrepancies are reported and resolved before use of the study intervention.
- Only participants enrolled in the study may receive study intervention. Only authorized study personnel may supply, prepare, or administer study intervention; the only exception is when study intervention is being self- or caregiver-administered. At the study site, all study intervention must be stored in a secure, environmentally controlled, and monitored (manual or automated) area in accordance with the labeled storage conditions with access limited to the investigator and authorized study personnel.
- The investigator or authorized study personnel are responsible for study intervention accountability, reconciliation, and record maintenance (that is, receipt, reconciliation, and final disposition records).

Further guidance and information for the final disposition of unused study interventions will be provided by the sponsor.

The investigator or designee is also responsible for

- explaining the correct use of the study interventions
- verifying that instructions are followed properly
- maintaining accurate records of study intervention dispensing and collection, and
- returning all unused clinical trial material to Lilly or its designee at the end of the study.

Note: In some cases, sites may destroy the material if, during site selection, the evaluator has verified and documented that the site has appropriate facilities and written procedures to dispose of clinical trial materials.

Sponsor responsibilities

The sponsor or its designee will supply study interventions in accordance with current Good Manufacturing Practice.

Clinical trial materials will be labeled according to the country's regulatory requirements.

The sponsor or its designee will provide instructions about clinical trial material supplies and about the preparation and handling of study interventions.

6.3. Measures to Minimize Bias: Randomization and Blinding

Blinding will be maintained throughout the conduct of the study as described in the separate Unblinding Plan.

Method of treatment assignment

Assignment to the ISAs and to the treatment groups within the ISAs will be determined by a computer-generated random sequence using an IWRS. The randomization ratios are specified in the individual ISAs. At the inception of this protocol, there is a single ISA in which there is randomization to treatment groups in a 1:1 ratio. Subsequent ISAs will have randomization ratio details which will depend on anticipated timing of ISA entry, number of active ISAs, required number of participants to be assigned to an active treatment group in the ISA, and desired number of placebo participants to maintain the blind and minimize bias.

Emergency unblinding

Emergency unblinding for AEs may be performed through the IWRS. This option may be used ONLY if the participant's well-being requires knowledge of the participant's treatment assignment. All actions resulting in an unblinding event are recorded and reported by the IWRS.

The investigator has the sole responsibility for determining if unblinding of a participants' intervention assignment is warranted in case of an emergency. Participant safety must always be the first consideration in making such a determination. If the investigator decides that unblinding is warranted, it is the responsibility of the investigator to promptly document the decision and rationale and notify the sponsor as soon as possible.

Discontinuation after unblinding

A participant must be discontinued from study intervention if a participant's study treatment assignment is unblinded to blinded site personnel performing study assessments, including the investigator, or to the participant, unless there are ethical reasons for the participant to continue receiving study intervention. In such a case, the investigator must obtain specific approval from the sponsor's clinical research physician in order for the participant to continue receiving study intervention (see Section 7.1).

Additional measures to minimize bias

Additional measures to minimize bias may be described in the ISAs.

6.4. Study Intervention Compliance

Deviations from the prescribed dosage regimen should be recorded in the eCRF.

The investigator should verify that participants have the ability to understand and comply with study instructions. Before enrolling a participant, the investigator is responsible for discussing with the participant methods to attain high compliance with study procedures, including administration of study intervention.

If a participant is noncompliant with study procedures, administration of study intervention, or both, the investigator should assess the participant to determine the cause of the noncompliance and to educate or manage the participant as appropriate to improve compliance.

If, in consultation with Lilly or its designee, the noncompliance is deemed to be significant or if further noncompliance occurs, the participant may be permanently discontinued from study intervention or from the study (see Sections 7.1 and 7.2).

Additional measures

If there are additional measures to assure or assess compliance or adherence, they will be described in the ISAs.

6.5. Concomitant Therapy

Participants will be instructed to consult the investigator or other appropriate study site personnel before taking any new medications or nutritional supplements during the study. The sponsor's medical monitor should be contacted if there are any questions.

Recording of concomitant therapy

Any medication or vaccine (including over-the-counter or prescription medicines, vitamins, and/or herbal supplements) that the participant is receiving at the time of study entry or receives during the study must be recorded along with

- reason for use
- route of administration, and
- dates of administration, including start and end dates.

For allowed concomitant therapies which are standard of care for SLE (as listed below), dosage information will also be collected as well as reason for use and route and dates of administration.

Allowed concomitant therapy for SLE

Participants should maintain their usual medication regimen for SLE and for any other diseases throughout the study unless specifically excluded by entry criteria (see Section 5 of this master protocol and, if applicable, in the relevant ISA) or unless changes are explicitly required (see following text on dose adjustment for corticosteroids). Doses of these usual medications must be stable prior to randomization, as stated in the study entry criteria, and should remain stable during the treatment period unless adjustments are explicitly allowed, as stated herein or in the relevant ISA.

Permitted concomitant background standard-of-care medications for SLE can include any combination of these:

- NSAIDs
- a single antimalarial (such as hydroxychloroquine, chloroquine, or quinacrine)
- a single oral immunosuppressant from the following list: methotrexate, azathioprine, mycophenolate mofetil, or mizoribine; and
- a single type of systemic corticosteroid.

Dose adjustments for antimalarials and immunosuppressants

Doses of antimalarials and immunosuppressants should not be adjusted during the study's treatment period.

If	Then	Nonresponder
a participant requires initiation or increase	the participant may remain in the	Data from such participants
in the dosage of antimalarials and/or	study and continue receiving	will be analyzed as
immunosuppressants.	study intervention.	nonresponder data.

Dose adjustment for corticosteroids

See Section 6.5 of the relevant ISA.

Concomitant therapy after permanent discontinuation of study intervention

Standard-of-care therapy can be resumed or modified after the participant is permanently discontinued from the study intervention.

6.6. Dose Modification

Dose modifications, if allowed, are described in the relevant ISA.

6.7. Intervention after the End of the Study

Interventions available after the end of the study, if applicable, are described in the ISAs.

7. Discontinuation of Study Intervention and Participant Discontinuation/Withdrawal

The following sections describe reasons for

- temporary or permanent discontinuation of a participant's dosing (discontinuation of study intervention), and
- discontinuation (withdrawal) of a participant from the study.

For discontinuation of study sites, of ISAs, or of this master protocol as a whole, see Appendix 10.1, Section 10.1.9.

7.1. Discontinuation of Study Intervention

Continuing in the study after discontinuation of study intervention

A participant who prematurely discontinues dosing with study intervention is strongly encouraged to remain in the study for safety monitoring through the treatment period and posttreatment follow-up as per ISA requirements.

See this master protocol (Section 8) and the relevant ISA (Section 1.3 [SoA] and Section 8) for data to be collected at the time of discontinuation from the study intervention and for activities in the posttreatment follow-up period and for any further evaluations that need to be completed.

Possible reasons for discontinuation of study intervention

The following reasons for early **permanent** discontinuation of study intervention apply to any ISA conducted under this master protocol.

Note: For laboratory values that meet early permanent discontinuation thresholds, the study intervention should be discontinued unless, in the opinion of the investigator, the laboratory abnormality is due to intercurrent illness or another identified factor. After consultation with the sponsor's designated medical monitor, the participant may be able to continue receiving study intervention. Laboratory tests may be repeated within 1 week to confirm whether discontinuation criteria have been met. Furthermore, if study intervention is not discontinued because of intercurrent illness, the investigator must confirm that the laboratory value no longer meets early discontinuation thresholds after the resolution of the intercurrent illness or other identified factor.

Hepatic event or liver test abnormality

The study drug should be interrupted or discontinued if one or more of these conditions occur:

Elevation	Exception
ALT or AST >8 times ULN	54
ALT or AST >5 times ULN for more than 2 weeks	
ALT or AST >3 times ULN and either TBL >2 times ULN or INR >1.5	In participants with Gilbert's syndrome, doubling of direct bilirubin should be used for drug interruption/discontinuation decisions rather than TBL >2 times ULN.

Elevation	Exception
ALT or AST >3 times ULN with the appearance of fatigue, nausea, vomiting, right upper quadrant pain or tenderness, fever, rash, and/or eosinophilia (>5%)	
ALP >3 times ULN, when the source of increased ALP is the liver	
ALP >2.5 times ULN and TBL >2 times ULN	In participants with Gilbert's syndrome, doubling of direct bilirubin should be used for drug interruption/discontinuation decisions rather than TBL >2 times ULN.
ALP >2.5 times ULN with the appearance of fatigue, nausea, vomiting, right upper quadrant pain or tenderness, fever, rash, and/or eosinophilia (>5%)	
Source: FDA 2009 and other consensus guidelines, with min	or modifications.

Abbreviations: ALP = alkaline phosphatase; ALT = alanine aminotransferase; AST = aspartate aminotransferase; INR = international normalized ratio; TBL = total bilirubin; ULN = upper limit of normal.

Resumption of the study drug can be considered only in consultation with the Lilly-designated medical monitor and only if the liver test results return to baseline and if a self-limited nondrug etiology is identified.

Abnormal hematology lab values:

- o hemoglobin < 7.0 g/dL (< 70.0 g/L)
- \circ total white blood cell count (WBC) <1500 cells/ μ L (<1.50 × 10³/ μ L or <1.50 GI/L)
- o absolute neutrophil count (ANC) <600 cells/ μ L (<0.60 × 10³/ μ L or <0.60 GI/L)
- \circ absolute lymphocyte count (ALC) <250 cells/ μ L (<0.25 × 10³/ μ L or <0.25 GI/L)
- HBV or HCV: The participant tests positive for HBV DNA (see Section 8.2.7) and clinical
 assessment is consistent with HBV reactivation, or tests positive for HCV RNA
 (Section 8.2.8).

Note: The HBV DNA result is to be confirmed if initial positive test result is positive but below the level of quantification (Section 7.1.1). The participant is to be referred to, evaluated, and managed by a specialist physician with expertise in evaluation and management of viral hepatitis prior to discontinuation of any immunomodulatory and/or immunosuppressive therapy, including study intervention. The timing of discontinuation from study intervention relative to the initiation of any antiviral treatment for hepatitis is to be based on the recommendation of the consulting specialist physician, in conjunction with the investigator, and aligned with medical guidelines and standard of care.

Suicidal Ideation and Behavior: The participant answered "yes" to Question 4 or 5 on the
"Suicidal Ideation" portion of the C-SSRS, or answered "yes" to any of the suicide-related
behaviors on the Suicidal Behavior portion of the C-SSRS. The participant may be assessed
by a psychiatrist or other appropriately trained professional to assist the investigator in
deciding whether the participant should be discontinued from the study intervention.

Certain adverse events (AEs):

- The participant experiences a severe AE, an SAE, or a change in a laboratory value or an ECG finding (see Section 8.2.3) that, in the opinion of the investigator, merits the discontinuation of the study intervention and appropriate measures being taken. In this case, the sponsor's medical monitor is to be notified immediately, and the event is to be documented.
- The participant has a systemic hypersensitivity reaction. The investigator should consult the sponsor-designated medical monitor, in determining that such an event has occurred and whether the participant should be permanently discontinued from the study intervention.
- The participant develops a malignancy.
 - Exception: Participants may be allowed to continue to receive study intervention if they develop no more than 2 successfully treated nonmelanoma skin cancers during the study.
- The participant develops HIV or AIDS infection.
- The participant develops active TB or untreated LTBI (Section 8.2.6).
- Serious or opportunistic infections, as defined in Section 5.2.
- Unblinding: If an investigator, site personnel performing assessments, or participant is
 unblinded to the participant's randomly assigned intervention, the participant must be
 discontinued from the study intervention. In cases where there are ethical reasons to have
 the participant remain in the study, the investigator must obtain specific approval from
 Lilly or its designee for the participant to continue receiving the study intervention.
- **Pregnancy:** The participant becomes pregnant (Section 8.2.5.1).
- Participant decision: The participant requests to discontinue receiving the study intervention.
- **Participant noncompliance:** The investigator decides that the participant is noncompliant with study intervention administration or other study procedures; in this case, the participant may be discontinued from study intervention or from the study (Section 7.2).
- Participant with intolerable or exacerbating disease: A participant with increased disease activity should discontinue study intervention at the discretion of the investigator and receive standard-of-care treatment, which may include biologic therapies.

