8.2.9. Hepatic Safety Monitoring

Close hepatic monitoring

Laboratory tests (Appendix 10.6), including ALT, AST, ALP, TBL, direct bilirubin, gamma-glutamyl transferase, and creatine kinase, should be repeated within 48 to 72 hours to confirm the abnormality and to determine if it is increasing or decreasing, if 1 or more of these conditions occur:

If a participant with baseline results of	develops the following elevations:
ALT or AST <1.5 times ULN	ALT or AST ≥3 times ULN
ALP <1.5 times ULN	ALP ≥2 times ULN
TBL <1.5 times ULN	TBL ≥2 times ULN (except for patients with Gilbert's syndrome)
ALT or AST ≥1.5 times ULN	ALT or AST ≥2 times baseline
ALP≥1.5 times ULN	ALP ≥2 times baseline

Abbreviations: ALP = alkaline phosphatase; ALT = alanine aminotransferase; AST = aspartate aminotransferase; TBL = total bilirubin; ULN = upper limit of normal.

If the abnormality persists or worsens, clinical and laboratory monitoring, and evaluation for possible causes of abnormal liver tests should be initiated by the investigator in consultation with the Lilly-designated medical monitor. At a minimum, this evaluation should include physical examination and a thorough medical history, including symptoms, recent illnesses (for example, heart failure, systemic infection, hypotension, or seizures), recent travel, history of concomitant medications (including over-the-counter), herbal and dietary supplements, history of alcohol drinking and other substance abuse.

Initially, monitoring of symptoms and hepatic biochemical tests should be done at a frequency of 1 to 3 times weekly, based on the participant's clinical condition and hepatic biochemical tests. Subsequently, the frequency of monitoring may be lowered to once every 1 to 2 weeks, if the participant's clinical condition and lab results stabilize. Monitoring of ALT, AST, ALP, and TBL should continue until levels normalize or return to approximate baseline levels.

Comprehensive hepatic evaluation

A comprehensive evaluation should be performed to search for possible causes of liver injury if 1 or more of these conditions occur:

If a participant with baseline results of	develops the following elevations:
ALT or AST <1.5 times ULN	ALT or AST ≥3 times ULN with hepatic signs/symptoms ^a or ALT or AST ≥5 times ULN
ALP <1.5 times ULN	ALP ≥3 times ULN
TBL <1.5 times ULN	TBL ≥2 times ULN (except for patients with Gilbert's syndrome)

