9.3. Statistical Analyses

9.3.1. General Considerations

Statistical analysis of this study will be the responsibility of Eli Lilly and Company or its designee.

Unless otherwise indicated in ISA-specific analyses, the following general considerations apply to the analyses:

• No adjustments for multiplicity will be performed.

- Efficacy and PRO analysis models may contain the independent variables. These
 variables may include, but are not limited to, treatment group, ISA, baseline disease
 activity, and geographic region.
- Missing data for dichotomous responder endpoints will be imputed using the NRI method.
- Participants will be considered nonresponders if they
 - o do not meet all the clinical response criteria
 - o are noncompliant with concomitant medication rules (Section 6.5), or
 - permanently discontinue study intervention at any time before the end of the treatment period for any reason.

Additional imputation methods may be considered for all endpoint types. Additional
imputations will be specified in the ISAs.

Other models may also be considered for the analyses if deemed appropriate for an ISA. Details regarding additional models will be specified in the ISAs.

Changes to the data analysis methods

Any change to the data analysis methods described in this protocol will require an amendment to this protocol ONLY if it changes a principal feature of the protocol. Any other change to the data analysis methods described in the protocol, and the justification for making the change, will be described in the relevant SAP and in the CSR. Additional exploratory analyses of the data will be conducted as deemed appropriate.

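### Protocol Section 7.1 contradicts itself on liver-test stopping criteria: the general Note permits continued dosing where the hepatic text does not, and nothing says which governs

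*Protocol*

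**What the plan says.** Protocol Section 7.1 lists reasons for stopping study drug early and permanently. The list reaches the whole platform: these reasons for permanent "discontinuation of study intervention apply to any ISA conducted under this master protocol".

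A Note at the head of the list deals with any laboratory value that reaches a permanent-stop threshold. It says "the study intervention should be discontinued unless, in the opinion of the investigator, the laboratory abnormality is due to intercurrent illness or another identified factor". With the medical monitor consulted, the participant may stay on study drug. Once the illness or other factor has resolved, "the investigator must confirm that the laboratory value no longer meets early discontinuation thresholds".

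The hepatic criteria are the next item. Their lead-in reads "The study drug should be interrupted or discontinued if one or more of these conditions occur". The Exception column holds only a bilirubin substitution for Gilbert's syndrome, in two rows. Below the table, resumption needs the medical monitor and is possible "only if the liver test results return to baseline and if a self-limited nondrug etiology is identified".

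Section 9.3.1 counts as nonresponders those who "permanently discontinue study intervention at any time before the end of the treatment period for any reason", unless an ISA analysis says otherwise.

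**The concern.** The Note and the hepatic text stand next to each other, apply to the same kind of result, and lead to different actions. An investigator who attributes a liver-test elevation to an intercurrent illness can cite the Note for continuing to dose. Another investigator with the same patient can cite the hepatic text for interrupting. The rows concerned include ALT or AST above 3 times ULN together with raised bilirubin or INR. At that level a safety rule should not depend on which paragraph a site reads first.

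There is also a classification problem. The hepatic rows are listed as reasons for permanent discontinuation, yet they describe interruption and possible resumption. Several later rules depend on whether a stop counts as permanent.

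**Working it through.** No sample size, error rate or event count is involved, and the plan gives no figure to reproduce. The check sets the passages side by side.

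**Step 1. Does the Note reach the hepatic rows?** Its scope is laboratory values at permanent-discontinuation thresholds. The hepatic table sits in the permanent list and has seven rows. Five rest on laboratory values (one of these, ALP above 3 times ULN, also requires that the liver be the source). Two add symptoms or eosinophilia. The Note excludes none of them. On its wording it covers at least the five.

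**Step 2. Compare the two rules.**

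| | General Note | Hepatic text |
|---|---|---|
| Dosing while the value is abnormal | May continue if attributed to intercurrent illness or another identified factor | Interrupted or discontinued; no such exception |
| Recovery level | No longer meets the stopping thresholds | Back to baseline |
| When recovery applies | After the factor resolves; not a condition for doses given meanwhile | Before dosing resumes |
| Qualifying cause | Any identified factor | Self-limited and not drug-related |
| Medical monitor consulted | Yes | Yes |

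The rules agree only in the last row.

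**Step 3. A case on the protocol's own thresholds.** Take ALT above 5 times ULN for more than 2 weeks, attributed by the investigator to an identified intercurrent illness. Under the Note, dosing may go on without a gap, with later confirmation that the thresholds are no longer met. Under the hepatic text, dosing is interrupted or discontinued, and restarts only after return to baseline with a self-limited nondrug cause.

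**Step 4. Does any other passage settle it?** Section 7.1.1 has general wording on interruption for AEs or abnormal laboratory values, with no hepatic rule. Section 8.2.9 covers monitoring and evaluation. Section 8.2.9.1 refers back to 7.1. None gives an order of precedence.

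**Step 5. What depends on temporary or permanent?**
- Section 9.3.1: a permanent stop means nonresponse; an interruption or continued dosing does not by that rule.
- Section 9.3.2.1: for BT01, failing to complete the 24-week treatment period also means nonresponse.
- SAP Table 4.2: permanent treatment discontinuations due to an AE are tabulated.
- Section 8.2.9.1: a drug discontinuation for a hepatic event triggers extra hepatic data collection.

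**The case against.** The best defence is that a specific rule governs over a general one. The hepatic text is self-contained: it has its own triggers, exceptions, cause test and resumption rule. The hematology list has none of these, so the Note may have been written for it. The Note is also tied to permanent-stop thresholds, while the hepatic rows mention interruption. This is a plausible reading, but the protocol does not state it, and placing the Note directly above the hepatic rows in the permanent list points the other way.

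The defence is right on three matters. The hepatic lead-in says should, not must. A site that always stops breaches neither text, so the conflict is that one text permits what the other does not; no site is forced into a deviation. Both routes to further dosing pass through the medical monitor, which limits divergence between sites but gives the monitor no rule to apply.

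It can also be said that the hepatic text is staged (interrupt, then resume or stop) and that whether a stop proved permanent can be observed. That is fair, but the list heading still labels these rows permanent, and Section 7.1.1 does not mention them.

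Three stronger readings are tempting and are not supported:

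- **A conflict in repeat-test timing.** The Note says "Laboratory tests may be repeated within 1 week to confirm whether discontinuation criteria have been met", and Section 8.2.9 says tests "should be repeated within 48 to 72 hours to confirm the abnormality". The first is permissive, the second starts from lower triggers, and a test at 48 to 72 hours falls within a week. Following 8.2.9 satisfies both.
- **A roughly 4-fold gap in recovery level.** A reader might compare 7.9 times ULN, just under the highest ALT row, with the 2 times ULN limit in exclusion criterion 42 (7.9/2 = 3.95). But the Note refers to thresholds in the plural, so a value under one row may still meet another. Criterion 42 applies at Visit 1, whereas SAP Section 4.3 takes baseline as the last value before first dose, usually Visit 2. The criterion does not cap baseline.
- **A measurable shift in the efficacy result.** With about 45 per arm, one reclassified participant is 1/45 = 2.2 percentage points. That is a unit of arithmetic, not an estimate. No rate of such events is given, continued dosing does not make anyone a responder, and Section 9.3.1 and SAP Section 4.2 leave room for ISA-specific handling that is not in these documents.

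**Conclusion.** The contradiction is real and lies within Section 7.1. The Note permits dosing through a liver-test threshold that the hepatic text does not permit, and the two differ on recovery level and on the cause that qualifies. Separately, the hepatic rows are filed as permanent while describing interruption and resumption.

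This is first a participant-safety ambiguity, and it applies to every ISA. It has no numerical size: the documents do not allow the number of participants concerned to be worked out. Inconsistent use of the nonresponder rule is a secondary possibility and cannot be quantified.

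The conclusion rests on the wording of the master protocol and assumes that no ISA text, which is not available here, sets the order of precedence. It implies no view on which clinical rule is right.

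**What to change.** Reconcile the passages in Section 7.1:

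1. State in the Note whether it applies to the hepatic criteria.
2. State which text takes precedence for liver tests, so that one recovery condition and one cause condition apply.
3. State that a hepatic interruption followed by resumption is recorded as temporary withholding under Section 7.1.1, and only a stop without resumption as permanent discontinuation. Section 9.3.1 and the discontinuation tables can then be applied in the same way at every site.

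Which clinical rule stands is for the sponsor's safety physicians. The cost is a few sentences in a protocol amendment and a memo to sites, with no new visits, tests or participants.
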